7.3. Psychological Health (self-report)

- **Patient Health Questionnaire-9 (PHQ-9) {Kroenke, 2001, The PHQ-9}**. The Participant Health Questionnaire 9 is a standardized assessment instrument designed to screen, diagnose, monitor, and measure the severity of depression.
- **Columbia Suicide Severity Rating Scale (C-SSRS) {Posner, 2011, The Columbia-Suicide Severity Rating Scale: initial validity and internal consistency findings from three multisite studies with adolescents and adults}**. The C-SSRS is a standardized assessment instrument designed to assess the presence and severity of suicidal ideation and behavior, identify those at risk, and track response to treatment. It has three main sections that evaluate suicidal ideation, the intensity of ideation and suicidal behavior. The first section, suicidal ideation, assesses risk ranging from a death wish or unspecific suicidal thoughts to active ideation with specific plans. In the second section the severity of ideation is evaluated and takes into account the frequency, duration and controllability of suicidal thoughts as well as environmental and cultural deterrents and reasons for suicidal ideation. The third section evaluates actual suicidal behavior and asks if there was an actual attempt, interrupted attempt, aborted attempt or preparatory acts of behavior. It also asks whether there was active suicidal behavior at the time of assessment and, finally, if suicide was completed. A fourth section is only answered in case there was / were suicidal attempts and measures the lethality and potential lethality of each suicidal attempt and respective dates. The CCSRS is a widely-used instrument and is currently being utilized in other first-in-man DBS clinical trials. The C-SSRS will be administered during the pre-surgery baseline assessment and then at any follow-up visit **only if the participant screens positive for suicidal ideation/behavior on the PHQ-9** (i.e. score ≥ 1 on question 9).

7.4. Quality of Life (self-report)

- **Traumatic Brain Injury Quality of Life (TBI-QOL) {Tulsky, 2015, TBI-QOL: Development and Calibration of Item Banks to Measure Patient Reported Outcomes Following Traumatic Brain Injury}**. The TBI-QOL was developed as a comprehensive patient-reported outcomes (PRO) measurement system specifically for individuals with TBI. It consists of 20 independent calibrated item banks and 2 uncalibrated scales that measure physical, emotional, cognitive, and social aspects of health-related quality of life. We will administer the short form (6-10 questions each) of the TBI-QOL Fatigue, Attention/Concentration, and Executive Function subscales.

7.5. Global Functional Outcome Measure

- **Glasgow Outcome Scale – Extended (GOSE) {Wilson, 1998, Structured interviews for the Glasgow Outcome Scale and the extended Glasgow Outcome Scale: guidelines for their use}**. The Glasgow Outcome Scale Extended (GOSE) is a measure of disability and handicap intended for use following head injury. The

GOSE subdivides the upper three categories of the original Glasgow Outcome Scale (GOS), severe disability, moderate disability and good recovery, into an eight-category scale: dead, vegetative state, lower severe disability, upper severe disability, lower moderate disability, upper moderate disability, lower good recovery, and upper good recovery to provide more detailed assessment of the functional effects of the injury. A structured interview has been developed to standardize assignment of an outcome category (Wilson et al. 1998).

7.6. Participant Interview

- A structured interview will be administered to obtain information about preinjury medical and social history, and level of social, educational and vocational function.

7.7. Exploratory Measures

7.7.1. Electrophysiological

Each enrolled participant will have electroencephalogram (EEG) studies obtained several times during the course of the study following DBS implantation. The initial EEG recording will be made on the day of admission for surgery. EEG recordings will be obtained using an EGI system (129 scalp sites using the Geodesic EEG Net Station (EGI, Eugene, OR) with the 129-channel Geodesic Sensor Net (Tucker 1993 [33]). For each recording session 5 minutes of resting baseline will be obtained at the beginning and end of the session. In addition, subjects will perform the Attention Network Test paradigm, a standard measure for assessment of attention that has been normed in the study population (Fan et al. 2002 [8]). The ANT will be presented using Eprime (Psychology Software Tools) on a standard flat screen monitor and the total duration of each ANT experimental session will be approximately 25 min. Local thalamic recordings will be recorded using the Percept PC system during the performance of the Attention Network Task.

To measure local population dynamics within the central thalamus during stimulation conditions in clinic we will record a differential signal on pairs of open channels adjacent to the channel used for stimulation using the Percept PC system. We will record up to 6 channels during OFF stimulation periods and 2 channels during stimulation. We will use a sampling rate of 250Hz (to optimize recording against known noise characteristics of the device) and filtered (4Hz to 100Hz) in compressed format. To characterize the EEG activation profiles we will use monopolar and bipolar stimulation through each contact individually and pairs of contacts in ON/OFF blocks of 5-10 second stimulation periods interleaved to obtain a minimum of 100 seconds of recording per condition with matched adjacent resting periods.

A similar approach will be used to collect behavioral, EEG and local thalamic recording data during performance of the Attention Network Task (Fan et al. 2002). EEG and local thalamic recordings will be synchronized using brief 1-2 second 20Hz pulses at the start and end of recording sessions. We will compare behavioral and EEG effects during interleaved blocks of 10 minutes of continuous ANT performance. Monopolar review for side effects will be completed prior to behavioral testing with the ANT.

We will use the sensing recording capabilities of the Percept PC to obtain longitudinal samples of brain activity during sleep-wake cycles in between outpatient office visits. Recordings with the device will occur as described above and as follows. Uniformly sampled and bandpassed

power will be obtained from one channel per electrode every ten minutes over 2 months. These data are stored on the device and will be downloaded at patient visits during the trial. We will evaluate the time domain recordings with spectral analysis.

8. EARLY WITHDRAWAL OR TERMINATION

Subjects will be informed that they may withdraw or be discontinued (early termination) from this study at any time. Further, they will be informed that the Investigator may withdraw them if they fail to comply with the study requirements or if the investigator feels it is in the best interest of the subject to discontinue their participation. The reason(s) for withdrawal or early termination will be documented on the appropriate page of the CRF. No further study assessments will be performed after the subject has withdrawn.

Subjects who consent to participate but do not receive the DBS device will not count towards the 6 patients limit for this study and new patients will be screened. No attempt will be made to replace subjects who are withdrawn or prematurely discontinue their study participation after the device has been implanted.

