6.1.3. Concomitant Medications

Subjects who are on centrally-acting medications will remain eligible for enrollment as long as the dose of the medication has been stable for at least three months prior to the date of enrollment. All concomitant medication and concurrent therapies will be documented during the Baseline Visit, and at every subsequent study visit. At each study visit, the Study Coordinator will review and print the list of concomitant medications that were completed at the participant's prior visit in order to accurately review and document changes in the participant's concomitant medications or concurrent therapies. The generic name of the drug, presence/absence of the drug at the time of randomization, date started, dose, route, unit frequency of administration (i.e., schedule) and the date stopped or changed will be recorded. We will also record whether the medication was prescribed to treat an AE (and, if so, the date of the AE form) or a new clinical

problem that arose after enrollment. The same information will be recorded for non-pharmacologic therapies, with the exception of dose and route of administration.

If there are any changes in a centrally-acting medication, or if a new centrally-acting medication is added following randomization, the Study Coordinator will apprise the Sponsor and a protocol violation will be recorded. The Sponsor will evaluate the potential influence of the new medication on the study treatment and will make a disposition regarding continued participation in the trial. Any disposition recommending withdrawal from the trial will be reviewed by the Clinical Oversight Committee (see [Section 10](#) below) before any action is taken.

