6.3. Randomization to Multiple Baseline Condition and Treatment Withdrawal

Following study enrollment, participants will be randomly assigned to 1 of 3 baseline conditions lasting 30, 44, or 58 days. Two participants will be assigned per condition. The staggered baseline schedule will enable assessment of CT-DBS effects within individual subjects and across subject pairs. Each participant will also be randomly assigned to a treatment withdrawal or continuation condition. Neither the investigator nor the participant will have knowledge or be apprised as to whether DBS is on or off during this period. For participants assigned to the treatment withdrawal condition, DBS will be switched off for 21 days (on days 170, 184, and 198 for cohorts 1-3, respectively) immediately after completing the 90-day unblinded treatment phase. Participants randomized to the continuation condition will continue to receive stimulation 12 hours per day over the same 21-day period. Upon conclusion of the 21-day treatment withdrawal phase, participants will undergo a final re-assessment on the multi-dimensional outcome assessment battery and on the electrophysiologic measures (on day 191, 205, or 219, depending on cohort). Currently there are no known safety issues related to withdrawing stimulation. The purpose of this follow-up visit is to determine if there is evidence of loss of effect in those assigned to the treatment withdrawal condition, and to evaluate the influence of

intervening factors on the effectiveness of DBS. The trial will be considered complete at the end of the treatment withdrawal phase.

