6.7. Post-Surgical Washout Phase

Participants will enter the washout phase following hospital discharge. The length of the baseline will be staggered for each participant pair. The purpose of this phase is twofold: (1) to provide a 30-day surgical washout for resolution of any transient physiological or behavioral effects of surgery and (2) to detect the temporal onset of the stimulation effects for each subject, should these occur at the time of stimulation titration onset. At the end of the surgical washout period, the multidimensional outcome assessment battery that was administered during the pre-surgical baseline phase will be repeated to assess for any changes in function before CT-DBS is switched on (see *Description of Outcome Assessments* below). A CT scan will be performed on day 65 to assess the final lead location, after any post-surgical changes have been allowed to resolve.

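### Section 8 ends all assessments on withdrawal, on its natural reading even when the investigator removes a consenting implanted participant, so removal during the 21-day blinded phase loses the closing battery and later safety visits

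*Combined protocol and SAP*

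**What the plan says.** Section 8 gives two routes out of the study. Either the participant leaves, or the investigator removes the participant. One ground for removal is non-compliance: "the Investigator may withdraw them if they fail to comply with the study requirements". The other ground is a judgement about the participant's welfare, worded as "if the investigator feels it is in the best interest of the subject to discontinue their participation". A single rule follows: "No further study assessments will be performed after the subject has withdrawn". The next paragraph adds: "No attempt will be made to replace subjects who are withdrawn or prematurely discontinue their study participation after the device has been implanted".

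Section 6.3 describes the blinded phase. For 21 days after the 90-day unblinded treatment, participants have stimulation switched off or continued, by random assignment. At the end, "participants will undergo a final re-assessment on the multi-dimensional outcome assessment battery". The aim is explicit: "The purpose of this follow-up visit is to determine if there is evidence of loss of effect in those assigned to the treatment withdrawal condition".

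Section 6.7 places an earlier battery at the end of the surgical washout; it "will be repeated to assess for any changes in function before CT-DBS is switched on". Section 6.11 schedules visits at months three and six, both covering general health, with neuropsychological status at month six. Section 6.12 allows unscheduled visits at the sponsor-investigator's discretion. After a change in centrally acting medication, section 6.1.3 says: "Any disposition recommending withdrawal from the trial will be reviewed by the Clinical Oversight Committee". Section 11 plans descriptive and exploratory analysis and gives no rule for missing data.

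**The concern.** The rule treats leaving the study and being taken off the assigned condition as one event, and stops data collection in either case. Nobody who has withdrawn consent should be tested further. A participant removed for non-compliance, a medication change or best interest may, however, be willing to be tested and may still carry the implant.

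The 21-day phase is the only one that the plan describes as blinded, and section 6 presents blinded withdrawal as a design feature meant to limit examiner and participant bias. Its closing battery is a single observation per person in a study of six. If it is not taken, it cannot be recovered. The same rule also ends planned health follow-up of an implanted person in a study whose safety endpoints are adverse-event rates.

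**Working it through.** **1. The schedule.** Stimulation starts on day 66, 80 or 94 (section 6.8). Titration lasts 14 days (6.8), treatment 90 days (6.9) and the blinded phase 21 days (6.3).

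- Cohort 1: 66 + 14 + 90 = 170; 170 + 21 = 191
- Cohort 2: 80 + 14 + 90 = 184; 184 + 21 = 205
- Cohort 3: 94 + 14 + 90 = 198; 198 + 21 = 219

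These reproduce the days stated in section 6.3. Removal between days 170 and 191, 184 and 205, or 198 and 219 comes before the closing battery. The month-3 and month-6 visits come later still, because three months after treatment is beyond the 21 days.

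**2. Which assessments could stand in for the lost one.**

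- Pre-operative baseline (6.5): before implantation.
- End of washout (6.7): stimulation OFF, but before any treatment, so it cannot show loss of a treatment effect.
- End of the 90 days (6.9): stimulation ON.
- End of the 21 days (6.3): OFF for those randomised to withdrawal, ON for those randomised to continuation.
- Month 6 (6.11): open label, no OFF condition specified, and itself barred after withdrawal.

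Only the fourth gives an OFF score after treatment. No section provides an early-termination battery.

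**3. Whether the rule covers removal by the investigator.** The barring sentence speaks of the subject having withdrawn, which could be limited to the participant's own decision. The same paragraph, however, also uses the verb for the investigator's act and gives no separate rule for it. The wider reading is the natural one, though it remains an interpretation.

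**4. Size of one loss.** One participant is 1/6 = 16.7% of the study. The plan does not state how many are assigned to each condition, so I assume 2, 3 or 4 OFF. One lost OFF score is then 1/2 = 50%, 1/3 = 33.3% or 1/4 = 25% of that group's end-of-phase data. If the person lost was continuing stimulation, the ON comparator group of 4, 3 or 2 loses 25%, 33.3% or 50%.

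**5. Direction.** If removal is unrelated to how the participant is doing, information is lost without bias. If a participant is removed because of worsening while OFF, the remaining OFF scores understate loss of effect. Section 9.4.1 lists rebound worsening on stopping stimulation among expected effects, so the second case is conceivable. The documents do not show how likely either is.

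**The case against.** A reader might infer that the rule biases the blinded comparison by removing exactly those who deteriorate when OFF. The documents do not support that as a finding. The ordinary response to worsening is to restart stimulation, and section 9.5 treats this as something other than study exit: it records whether study treatment was changed because of an adverse event and refers to breaking the blind at the treating physician's judgement. Neither provision says that the participant is then withdrawn. If the participant stays in the study, section 8 is not triggered and the closing battery is still due. This objection stands, and it reduces bias to a possibility.

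Four further objections carry weight.

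- **Discretion before removal.** Section 8 bars assessments only after withdrawal. The investigator controls the timing of a removal and can call a 6.12 visit beforehand, and a medication-related removal waits for committee review. What remains is that nothing requires the battery to be given.
- **Likely rarity.** The window is 21 days, and section 6.3 reports no known safety issue with withdrawing stimulation.
- **Stage of the trial.** Section 6.6.1 draws on the first five patients and plans the implantation of the final one. Five of six therefore appear to have been implanted already. How many had completed the blinded phase or follow-up is not stated.
- **Limits of the remedy.** A battery kept after a restart is an ON score, so the full 21-day OFF value is preserved only when a removed participant stays OFF.

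These objections limit the reach of the point. They do not supply a reason to stop testing a participant who still consents.

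**Conclusion.** The point holds as a minor one. On its natural reading, section 8 discards the closing battery of the only blinded phase, and the later general-health visits, for a consenting implanted participant whom the investigator removes during the 21 days. The loss is 1 of 6 participants per case; under an assumed 2, 3 or 4 participants OFF, it is 25% to 50% of the OFF scores if that participant was OFF.

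Three stronger readings should be set aside. Not everyone removed loses an OFF score, since continuation participants lose an ON comparator. The 90-day result is not affected. Bias towards understating loss of effect is not shown, because restarting stimulation need not mean leaving the study. What is established is avoidable loss of information and of safety follow-up, if such a removal occurs. The conclusion rests on reading section 8 as covering investigator removal. It matters only for participants who have yet to finish the phase or follow-up.

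**What to change.** Amend section 8 so that, unless the participant withdraws consent, neither a stop or change in stimulation nor removal by the investigator ends the scheduled end-of-phase battery or the section 6.11 visits. Where it is safe, give the battery at a 6.12 visit before stimulation is restarted or the participant is removed. Label it with the number of days OFF and the actual stimulation status, entered after testing so that the assessor stays blinded. Report results by assigned condition, with such cases flagged. If the sponsor intended section 8 to apply only to participants who leave by their own choice, saying so in that sentence would settle the reading.

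The cost is one or two sentences, written FDA and IRB approval under section 13.5 if the change counts as substantive, and rarely one extra battery. A battery given during an adverse event may be hard to interpret. An early or post-restart score does not replace a 21-day OFF value, and the label and flag make that plain.

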9. ADVERSE EVENTS

9.1. Adverse Event Identification and Assessment

An adverse event is any undesirable clinical occurrence in a participant during the clinical investigation, having been absent at baseline (or, if present at baseline, appears to worsen), whether or not it is considered to be related to the device or to stimulation. The investigator will not be required to record transient stimulation-induced neurological effects (e.g., paresthesias) or findings within normal expected postoperative outcomes. For example, postoperative pain that is not outside expected levels will not be recorded as an adverse event. Postoperative events that involve a clinically significant severity of symptoms, duration of symptoms, or that require deviation from usual postoperative clinical interventions (e.g., pain lasting longer than expected and requiring long-term opioid use) will be recorded as adverse events. The testing of DBS in MCS subjects did not identify any adverse events that are specific to brain injured subjects.

9.2. Adverse Device Effect

An adverse device effect is a device related adverse event. During this clinical investigation an event should be considered related to the device when it is the result of:

- The implanted components (lead, extension, neurostimulator)
- The implant procedure
- Programming
- Stimulation

A non-related event is one that results from:

- A patient related condition
- Concomitant medication

- Other (specify)

The relationship or association of the AE to the study product will be characterized by the Investigator as one of the following in [Table 2](#).

Table 2: AE Relationship to Device

Relationship	Definition
Not related	There is no temporal relationship between the study product/treatment and the event, which makes a causal relationship clearly and incontrovertibly due to extraneous causes, i.e. not related to the study product.
Unlikely	Other factors, such as concurrent illness, progression or expression of a disease, or a reaction to a concomitant medication are more likely the cause of the event. It is improbable that the study product/treatment caused the AE.
Possibly	The AE cannot be fully explained by other causes, and it is possible that the study product/treatment caused the event.
Probably	A reasonable temporal association exists between the AE and the study product/treatment, and, based upon the investigator's clinical experience, the association of the AE with the study product/treatment seems probable.
Definitely	A definite or certain temporal association exists between the AE and the study product/treatment, and, based upon the investigator's clinical experience, the association of the AE with the study product/treatment seems definite or certain.

9.3. Serious Adverse Events (SAEs)

A serious adverse event is one that meets any of the following criteria (ICH Good Clinical Practice Guideline, April 1996, Section 1.50):

- Results in death
- Is life threatening
- Requires inpatient hospitalization or prolongation of existing hospitalization
- Results in persistent or significant disability/incapacity
- Is a congenital anomaly/birth defect

Events that do not meet these criteria are considered non-serious

A planned hospitalization for pre-existing condition, or a procedure required by the Clinical Investigation Plan, without a serious deterioration in health, is not considered to be a serious adverse event.

